### **10.3.14. Study and Site Start and Closure**

#### **First Act of Recruitment**

The first participant screened is considered the first act of recruitment and it becomes the study start date.

#### **Study/Site Termination**

The sponsor reserves the right to close the study site or terminate the study at any time for any reason at the sole discretion of the sponsor. Study sites will be closed upon study completion. A study site is considered closed when all required documents and study supplies have been collected and a study site closure visit has been performed.

The investigator may initiate study site closure at any time, provided there is reasonable cause and sufficient notice is given in advance of the intended termination.

Reasons for the early closure of a study site by the sponsor or investigator may include but are not limited to:

- Failure of the investigator to comply with the protocol, the requirements of the IEC/IRB or local health authorities, the sponsor's procedures, or GCP guidelines
- Inadequate recruitment of participants by the investigator
- Discontinuation of further study vaccine development

## **10.4. Appendix 4: Adverse Events, Serious Adverse Events, Product Quality Complaints, and Other Safety Reporting: Definitions and Procedures for Recording, Evaluating, Follow-up, and Reporting**

### **10.4.1. Adverse Event Definitions and Classifications**

#### **Adverse Event**

An AE is any untoward medical occurrence in a clinical study participant administered a pharmaceutical (investigational or non-investigational) product. An AE does not necessarily have a causal relationship with the intervention. An AE can therefore be any unfavorable and unintended sign (including an abnormal finding), symptom, or disease temporally associated with the use of a medicinal (investigational or non-investigational) product, whether or not related to that medicinal (investigational or non-investigational) product. (Definition per International Council on Harmonisation [ICH])

This includes any occurrence that is new in onset or aggravated in severity or frequency from the baseline condition, or abnormal results of diagnostic procedures, including laboratory test abnormalities.

Note: For time period of sponsor's AE collection, see All Adverse Events under Section 8.3.1.

#### **Serious Adverse Event**

An SAE based on ICH and EU Guidelines on Pharmacovigilance for Medicinal Products for Human Use is any untoward medical occurrence that at any dose:

- Results in death
- Is life-threatening  
(The participant was at risk of death at the time of the event. It does not refer to an event that hypothetically might have caused death if it were more severe.)
- Requires inpatient hospitalization or prolongation of existing hospitalization
- Results in persistent or significant disability/incapacity
- Is a congenital anomaly/birth defect
- Is a suspected transmission of any infectious agent via a medicinal product
- Is Medically Important\*

\*Medical and scientific judgment must be exercised in deciding whether expedited reporting is also appropriate in other situations, such as important medical events that may not be immediately life-threatening or result in death or hospitalization but may jeopardize the participant or may require intervention to prevent one of the other outcomes listed in the definition above. These should usually be considered serious.

If a serious and unexpected AE occurs for which there is evidence suggesting a causal relationship between the study vaccine and the event (eg, death from anaphylaxis), the event must be reported

as a SUSAR by the sponsor to health authorities and by the investigator to the IEC/IRB according to regulatory and local requirements.

### **Unlisted (Unexpected) Adverse Event/Reference Safety Information**

An AE is considered unlisted if the nature or severity is not consistent with the applicable product reference safety information. Ad26.RSV-A.preF, RSV-A preF protein, Ad26.RSV-B.preF2, and RSV-B preF protein, the expectedness of an AE will be determined by whether or not it is listed in the IB ([IB Ad26/protein preF RSV vaccine 2021](#), [IB VAC18195 2021](#)).

#### **10.4.2. Attribution Definitions**

##### **Assessment of Causality**

The causal relationship to study vaccine is assessed by the investigator. The following selection must be used to assess all AEs.

##### **Related**

There is a reasonable causal relationship between study vaccine administration and the AE.

##### **Not Related**

There is not a reasonable causal relationship between study vaccine administration and the AE.

The term "reasonable causal relationship" means there is evidence to support a causal relationship.

By definition, all solicited AEs at the injection site (local) will be considered related to the study vaccine administration.

#### **10.4.3. Severity Criteria**

All AEs and laboratory data will be coded for severity using a modified version of the FDA grading table, based on version of September 2007 ([FDA 2007](#)), included in [Appendix 6](#), Toxicity Grading Scale.

For AEs not identified in the grading table, the following guidelines will be applied:

|                |                              |                                                                                                                                                                                                      |
|----------------|------------------------------|------------------------------------------------------------------------------------------------------------------------------------------------------------------------------------------------------|
| Grade 1 | Mild                         | Symptoms causing no or minimal interference with usual social and functional activities                                                                                                              |
| Grade 2 | Moderate                     | Symptoms causing greater than minimal interference with usual social and functional activities                                                                                                       |
| Grade 3 | Severe                       | Symptoms causing inability to perform usual social and functional activities and requires medical intervention                                                                                       |
| Grade 4 | Potentially life-threatening | Symptoms causing inability to perform basic self-care functions OR medical or operative intervention indicated to prevent permanent impairment, persistent disability OR ER visit or hospitalization |

The severity of solicited signs and symptoms will be graded in the diary by the participant based on the severity assessment provided in the diary and then verified by the investigator using the toxicity grading scale in [Appendix 6](#). (Note: severity of the measured events will be derived from the diameter [for erythema and swelling] and the temperature measurements [for fever])

#### 10.4.4. Special Reporting Situations

Safety events of interest on a sponsor study vaccine in an interventional study that may require expedited reporting or safety evaluation include, but are not limited to:

- Overdose of a sponsor study vaccine
- Suspected abuse/misuse of a sponsor study vaccine
- Accidental or occupational exposure to a sponsor study vaccine
- Medication error, intercepted medication error, or potential medication error involving a Johnson & Johnson medicinal product (with or without patient exposure to the Johnson & Johnson medicinal product, eg, product name confusion, product label confusion, intercepted prescribing or dispensing errors)
- Exposure to a sponsor study vaccine from breastfeeding
- Reporting of participant pregnancy or participant partner(s) pregnancy

Special reporting situations must be recorded in the eCRF. Any special reporting situation that meets the criteria of an SAE must be recorded on the SAE page of the eCRF.

#### 10.4.5. Procedures

##### All Adverse Events

All AEs, regardless of seriousness, severity, or presumed relationship to study vaccine, must be recorded using medical terminology in the source document and the eCRF. Whenever possible, diagnoses should be given when signs and symptoms are due to a common etiology (eg, cough, runny nose, sneezing, sore throat, and head congestion should be reported as "upper respiratory

infection"). Investigators must record in the eCRF their opinion concerning the relationship of the AE to study therapy. All measures required for AE management must be recorded in the source document and reported according to sponsor instructions.

For all studies with an outpatient phase, including open-label studies, the participant must be provided with a "wallet (study) card" and instructed to carry this card with them for the duration of the study indicating the following:

- Study number
- Statement, in the local language(s), that the participant is participating in a clinical study
- Investigator's name and 24-hour contact telephone number
- Local sponsor's name and 24-hour contact telephone number (for medical personnel only)
- Site number
- Participant number
- Any other information that is required to do an emergency breaking of the blind

### **Serious Adverse Events**

All SAEs that have not resolved by the end of the study, or that have not resolved upon the participant's discontinuation from the study, must be followed until any of the following occurs:

- The event resolves
- The event stabilizes
- The event returns to baseline, if a baseline value/status is available
- The event can be attributed to agents other than the study vaccine or to factors unrelated to study conduct
- It becomes unlikely that any additional information can be obtained (participant or health care practitioner refusal to provide additional information, lost to follow-up after demonstration of due diligence with follow-up efforts)

Any event requiring hospitalization (or prolongation of hospitalization) that occurs during participation in the study must be reported as an SAE, except hospitalizations for the following:

- Hospitalizations not intended to treat an acute illness or AE (eg, social reasons such as pending placement in long-term care facility)
- Surgery or procedure planned before entry into the study (must be documented in the eCRF). Note: Hospitalizations that were planned before the signing of the ICF, and where the underlying condition for which the hospitalization was planned has not worsened, will not be considered SAEs. Any AE that results in a prolongation of the originally planned hospitalization is to be reported as a new SAE.

The cause of death of a participant in a study during the entire study period, whether or not the event is expected or associated with the study vaccine, is considered an SAE.

Information regarding SAEs will be transmitted to the sponsor using an SAE reporting form and safety report form of the eCRF, which must be completed and reviewed by a physician from the study site, and transmitted in a secure manner to the sponsor within 24 hours. The initial and follow-up reports of an SAE should be transmitted in a secure manner electronically or by facsimile (fax). Telephone reporting should be the exception and the reporter should be asked to complete the appropriate form(s) first.

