- j. Investigator must check for clinically significant acute illness at the time of vaccination or body temperature of  $\geq 38.0^{\circ}\text{C}$  ( $\geq 100.4^{\circ}\text{F}$ ) within 24 hours prior to the planned time of vaccination. In such cases, the participant may be vaccinated up to, and no later than 10 days after the scheduled vaccination, or be withdrawn at the discretion of the investigator.
- k. Blood sample volumes are approximate. Refer to the laboratory manual for additional details.
- l. Aliquots of serum samples collected for immunogenicity test can be reconverted for participant's safety purposes upon sponsor request. Please refer to [Appendix 2](#) for a non-exhaustive list of tests that will be requested on these samples in case of potential AESI reporting.
- m. Blood for humoral immune responses will be drawn from all participants. Blood for cellular immune responses will be drawn from a subset of participants (from Cohorts 1, 2, and 3; not applicable to Cohort 4).
- n. Based on results available at the time of primary analysis, the sponsor will decide which arms will continue with blood sampling for cellular immune responses beyond 6 months post vaccination in Cohorts 1 and 2.
- o. After vaccination, participants will remain under observation at the study site for at least 30 minutes for presence of any acute reactions and solicited events. Any unsolicited AEs, solicited local (injection site) or systemic AEs, and vital signs (sitting systolic and diastolic blood pressure, heart rate, and respiratory rate after at least 5 minutes rest, and body temperature) will be documented by the study site personnel following this observation period.
- p. All (S)AEs and special reporting situations related to study procedures or to non-investigational (concomitant) Janssen products will be collected from ICF signature onwards until the end of the study for all participants. All other SAEs and AESIs will be collected from administration of study vaccine (Day 1) until 6 months after the last study vaccination. AEs leading to discontinuation from vaccination and/or study will be collected for the duration of the study.
- q. AESIs, including potential AESIs, are to be reported from the moment of vaccination until 6 months after the last study vaccination.

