#### **8.3.1. Time Period and Frequency for Collecting Adverse Event, Serious Adverse Event and Adverse Event of Special Interest Information**

##### **All Adverse Events**

AEs and special reporting situations, whether serious or non-serious, that are related to study procedures or that are related to non-investigational sponsor products will be reported from the time a signed and dated ICF is obtained until the end of the study/early withdrawal.

Clinically relevant medical events not meeting the above criteria and occurring between signing of ICF and moment of first vaccination will be collected on the Medical History eCRF page as pre-existing conditions.

Solicited AEs, collected through a participant diary, will be recorded for each vaccination from the time of vaccination until 7 days post-vaccination.

All other unsolicited AEs and special reporting situations, whether serious or non-serious, will be reported for each vaccination from the time of vaccination until 28 days post-vaccination. Unsolicited AEs with the onset date outside the timeframe defined above (>28 days after previous study vaccination), which are ongoing on the day of the subsequent vaccination, should be recorded as such.

All SAEs and AEs leading to discontinuation from the study (regardless of the causal relationship) and all AESIs are to be reported from the moment of vaccination until 6 months post vaccination. The sponsor will evaluate any safety information that is spontaneously reported by an investigator beyond the time frame specified in the protocol.

All COVID-19 cases will be collected for all participants for the duration of the study.

See Section 7.2 for procedures associated with withdrawal of consent.

All AEs will be followed until resolution or until clinically stable.

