### **Serious Adverse Events**

All SAEs occurring during the study must be reported to the appropriate sponsor contact person by study site personnel immediately, but no later than within 24 hours of their knowledge of the event.

Information regarding SAEs will be transmitted to the sponsor using the Serious Adverse Event Form and Safety Report Form of the eCRF, which must be completed and reviewed by a physician from the study site, and transmitted to the sponsor immediately, but no later than within 24 hours. The initial and follow-up reports of an SAE should be transmitted electronically or by facsimile (fax). Telephone reporting should be the exception and the reporter should be asked to complete the appropriate form(s) first.

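### The protocol gives incompatible time windows for SAE reporting, so late SAE counts depend on which passage a site follows

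*Protocol*

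**What the plan says.** Two passages set no end date short of the end of the study.

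- Protocol 8.3.1, Serious Adverse Events: "All SAEs occurring during the study must be reported to the appropriate sponsor contact person by study site personnel immediately".
- Protocol 10.4.5, Serious Adverse Events: a hospitalization "that occurs during participation in the study must be reported as an SAE, except hospitalizations for the following" two listed categories (not for an acute illness or AE; planned before entry). The same section counts as an SAE "The cause of death of a participant in a study during the entire study period", whether or not it is expected or related.

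Two passages set a 6-month limit, but not the same one.

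- Protocol 8.3.1, All Adverse Events: SAEs, AEs leading to discontinuation from the study, and AESIs "are to be reported from the moment of vaccination until 6 months post vaccination".
- Schedule of Activities, footnote p: "All other SAEs and AESIs will be collected from administration of study vaccine (Day 1) until 6 months after the last study vaccination". It keeps (S)AEs related to study procedures or concomitant sponsor products to the end of the study, and adds that "AEs leading to discontinuation from vaccination and/or study will be collected for the duration of the study".

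A note in 10.4.1 directs the reader: "For time period of sponsor's AE collection, see All Adverse Events under Section 8.3.1".

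In the SAP, Section 5.3.2 plans safety summaries per phase and over the whole study and includes all SAEs. Section 5.3.2.2 lists tables of SAEs and of AEs leading to death. Section 5.9 plans yearly analyses and a final analysis with safety data to study end. Section 5.3.2.4 counts a participant with no reported event as having had none.

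**The concern.** Follow-up runs for 3 years in Cohorts 1 and 2, and for 5 years in Arms 11a, 11b, 12 and Cohort 4. Most of it falls after the 6-month limit, where the passages disagree. Once the 6-month post-vaccination visits are over, the Schedule of Activities types the remaining visits as immunogenicity only. Whether a late SAE is recorded then depends on which passage the site works from.

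If sites differ, late SAE counts mix complete with incomplete ascertainment. The SAP's missing-data rule turns each unreported late SAE into a non-event, so the whole-study percentages would be too low by an unknown amount. The note to the first pausing rule in Section 6.9 sends all deaths to the DRC for information, so the handling of late deaths matters there too.

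**Working it through.** The plan states no figure that can be reproduced here. The check is a comparison of texts, followed by the size of the disputed period.

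**Is the event reportable if it occurs more than 6 months after the last vaccination?**

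| Late event | 8.3.1 All Adverse Events | Footnote p | 8.3.1 Serious Adverse Events | 10.4.5 |
|---|---|---|---|---|
| Non-fatal hospitalization, not related to procedures or sponsor products, participant stays in study | No | No | Yes | Yes, unless excepted |
| Other non-fatal SAE, same conditions | No | No | Yes | No window stated |
| SAE related to procedures or non-investigational sponsor products | Yes | Yes | Yes | Yes, if a hospitalization |
| AE leading to study discontinuation | No | Yes | Only if serious | Only if a hospitalization or death |
| Fatal event | No | Yes, if handled as an AE leading to withdrawal (7.2 lists death as a reason) | Yes | Yes |

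Only the third row has no passage saying no. In the first two rows the 6-month and whole-study rules conflict outright. In the fourth, 8.3.1 All Adverse Events conflicts with footnote p. In the fifth, 8.3.1 All Adverse Events stands alone against the other three. So 8.3.1 sits on both sides of the conflict.

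The SAP does not settle the matter. In 5.3.2 the 6-month bracket follows the AESI terms, and it is unclear whether it also covers SAEs.

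**Size of the disputed period.** Inputs from the protocol design tables and durations:

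- Cohorts 1 and 2: 132 + 528 = 660 participants, 36 months each.
- Arms 10 and 13: 150 + 50 = 200 participants, 12 months each.
- Arms 11a, 11b, 12 and Cohort 4: 75 + 75 + 50 + 540 = 740 participants, 60 months each.
- Revaccination: at least 12 months after dose 1, exact time open. Assumed at month 12 (the minimum) or month 24.
- The window closes 6 months after the last vaccination, as in footnote p.

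Planned person-months: 660 × 36 + 200 × 12 + 740 × 60 = 23,760 + 2,400 + 44,400 = 70,560.

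Disputed person-months = Σ n × (follow-up − window end):

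- Month 12: 660 × 30 + 200 × 6 + 740 × 42 = 19,800 + 1,200 + 31,080 = 52,080, which is 4,340 person-years, or 52,080 / 70,560 = 73.8%.
- Month 24: 19,800 + 1,200 + 740 × 30 = 43,200, which is 3,600 person-years, or 61.2%.

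With 10% dropout per year (the Cohort 4 assumption in 9.2.4, applied here to every cohort), each month m, counted from 0, is weighted by 0.9^((m + 0.5)/12). The planned total becomes 57,163 person-months. The disputed part is 39,816 (69.7%) for month 12 and 32,620 (57.1%) for month 24.

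**The case against.** The best defence is that the 6-month limit governs and the other passages only set procedure. The note in 10.4.1 sends Appendix 4 readers to the paragraph with the 6-month limit. The endpoints use 6 months. The Serious Adverse Events paragraph of 8.3.1 is mainly about the 24-hour clock and the form, and 10.4.5 is headed as procedures. Section 8.3.1 also says the sponsor will evaluate information reported spontaneously after the time frame, which suggests that a limit was intended.

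This explains much of 8.3.1, but not the death sentence in 10.4.5, which states its own period. The pointer also leads to a paragraph that contradicts footnote p on AEs leading to study discontinuation. Spontaneous reporting is voluntary, so it does not make late counts complete.

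Other limits on the point stand. The 6-month SAE endpoints are untouched, and all analyses are descriptive. Site staff are planned to stay blinded to study end, so uneven reporting between sites is unlikely to differ by arm. The harm is to completeness of late counts more than to between-arm contrasts.

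A reader might infer more than the documents support:

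- *Late deaths are generally lost.* They are missed only by a site that follows 8.3.1 All Adverse Events. Section 10.4.5 captures them, and so can footnote p read with 7.2. Applying a mortality rate to the disputed person-years would therefore overstate the loss, and the documents give no such rate.
- *Footnote p ends all SAE collection, or 10.4.5 covers every hospitalization.* Both have stated exceptions.
- *Unrecorded deaths explain missing 5-year titres.* Nothing in the documents supports this.

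**Conclusion.** The point holds as a contradiction in the current text. It is clearest for late, non-fatal SAEs that are unrelated to study procedures or sponsor products and do not lead to discontinuation. For AEs leading to study discontinuation, 8.3.1 All Adverse Events and footnote p disagree directly.

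What is at risk is the completeness of late SAE and death counts in the whole-study, yearly and final tables. The disputed period is 3,600 to 4,340 planned person-years, 61% to 74% of planned follow-up, or 57% to 70% with 10% yearly dropout. These figures rest on the assumed revaccination times, and the last pair also on extending the Cohort 4 dropout rate to all cohorts. They measure exposure to the conflict, not the number of events that would be missed. The contradiction itself depends on none of these assumptions.

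**What to change.** Protocol: reconcile both paragraphs of 8.3.1, footnote p and 10.4.5 to one stated SAE window. The choice of window is the sponsor's. State explicitly how deaths and AEs leading to discontinuation after that window are recorded, and whether they go to the DRC under the note in 6.9.

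SAP 5.3.2: limit the SAE tables to the window in which SAEs are completely collected. If deaths are collected over the whole study, tabulate them separately.

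The cost is wording in one amendment and one SAP table, plus a little site recording if late deaths are kept.
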